8.5.2.c. Other Drug and Alcohol Use Assessment. Severity of cannabis and other substance use and its associated problems will be assessed at baseline and weeks 5,10, and 14 with the Addiction Severity Index (ASI, 5th edition) (McLellan et al. 1992), a widely-used and independently-validated interview that measures the severity of problems in 7 areas of functioning that are frequently affected in patients with SUDs: drug use, alcohol use, employment, legal status, medical condition, social functioning, and psychological status. In addition to our primary focus on marijuana use (urine screens plus days of use), we will examine other substance use (using urine screens plus days of other substance use). We will use this method to determine the number of days of marijuana use and of any substance use (and conversely, days of abstinence). We will examine ASI composite scores as secondary measures of substance use outcome. We will also use the self-administered Drug and Alcohol Use Questionnaire. This measure, administered at baseline, addresses the context of lifetime and recent drug and alcohol use, as well as sociodemographic data. At each treatment visit, patients will complete a brief Weekly Drug and Alcohol Use Inventory, indicating their number of days using marijuana, other drugs, and alcohol during the previous week. The Marijuana Goals Questionnaire (Griffin et al. 1989) is a brief guestionnaire administered at baseline to assess treatment goals, specifically, whether a subject is seeking abstinence or reduction in marijuana use. A 12-item self-administered questionnaire, the Marijuana Craving Questionnaire, will be used to assess craving at

Partners Human Subjects Research Application Form

baseline and weekly during treatment and at the 14-week follow-up visit (Heishman et al. 2009). A short form of the Marijuana Withdrawal Checklist will be used to assess withdrawal symptoms at baseline and weekly during treatment and at the 14-week follow-up visit (Budney et al. 1999). If there is a discrepancy among results obtained by these methods of substance use assessment, we will meet with the subject and have a conversation about their substance use. After the conversation, we will use our clinical judgment to determine the level of use that we believe is most accurate for that subject. A 6-page questionnaire that we created titled Marijuana Perceptions of Risk and Experiences (MPRE), will be distributed at baseline, and once during weeks 5, 10 and 14 to assess each participant's perceptions of cannabis risk/harm and his or her motivations to quit/continue using cannabis throughout the course of treatment.

- 8.5.3. Mood and Impulsivity Assessments. We will monitor subjects' mood and impulsivity throughout the study using 3 assessments. The Beck Anxiety Inventory (BAI) is a 21-item self-report measure that can be used to assess the severity of anxiety. The Quick Inventory of Depressive Symptomatology (QIDS-SR) is a short self-report questionnaire for depressive symptoms used successfully in the STAR*D project. The Barratt Impulsiveness Scale (BIS-11) is a commonly used tool to measure impulsivity in various neuropsychological disorders as well as in substance abuse. Three dimensions can be assessed using this scale, which include Cognitive Impulsivity, Motor Impulsivity, and Non-planning Impulsivity.
- 8.6. Medication Adherence Assessment. The proposed studies involve chronic administration of medication given under double-blind conditions. Three methods of medication adherence will be used as multiple methods are preferred (Weiss 2004): 1) pill counts will be made; 2) subjects will record when they take their capsules on the ActiWatch-Score device; 3) urinary riboflavin levels (a 25 mg dose will be given with each dose of medication) will be measured using a UV spectrophotometer. If there is a discrepancy among results obtained by these methods, we will meet with the subject and have a conversation about their medication adherence. After the conversation, we will use our clinical judgment to determine the level of adherence that we believe is most accurate for that subject.

8.8. Data Management

All data collected will be de-identified with subject ID numbers and used for research purposes only. Written records will be kept in a locked file cabinet in a locked office. They will be destroyed after 5 years. Computerized data files will also be de-identified with subject ID numbers and kept in a password protected file on a password protected computer.

8.9. Statistical Analysis

The primary data analysis will be an intent-to-treat analysis, which includes all randomized subjects. Of note, every attempt will be made to continue assessing subjects even if they drop out of treatment. In addition, we will replicate all analyses with the completers only. The primary and secondary outcome variables are intended to

Partners Human Subjects Research Application Form Version Date: July 26, 2016

explore various aspects of response to therapy and to help define a clinically meaningful response. The primary outcome measures, Actiwatch-scores, daily diaries, TLFB self-report data, in addition to quantitative urinary THC metabolites, have been chosen for their ability to indicate daily use of cannabis by relying on self-report of use.

Specifically, for assessing the effect of dronabinol and clonidine on cannabis use patterns, we propose to use the generalized estimating equations (GEE) approach to longitudinal analysis, appropriately accounting for the positive correlation among repeated urine screen assessments within the same individual.

Analyses of secondary substance use outcomes will focus on the number of days of cannabis use and of any substance use (and conversely, days of abstinence) during treatment and post-treatment follow-up. In addition, we will also examine the ASI Drug and Alcohol composite scores. Frequency of days of cannabis use (and any substance use and days of abstinence) will be analyzed via a log-linear (or Poisson) regression model, controlling for pre-treatment frequency of days of cannabis use. Although loglinear regression methods are considered appropriate for the analysis of count or frequency data, in many biomedical applications, count data have variability that far exceeds that predicted by the Poisson distribution; we expect that days of cannabis use (and any substance use and days of abstinence) will not be an exception. Linear mixed effects models will be used to examine the effect of treatment group on changes in the ASI Drug and Alcohol composite scores during treatment and post-treatment follow-up assessments (as determined by the group-by-time interaction in the linear mixed effects regression models). The linear mixed effects model will include random intercepts and slopes to appropriately account for correlation among repeated measures and heterogeneity of variance over time; the model will be fit using PROC MIXED in SAS.

In secondary analyses of mood outcomes, mood episodes will be assessed during treatment and post-treatment follow-up, using the QIDS-SR, , BAI, and BIS-11; ; changes in risk of mood episodes during treatment and post-treatment follow-up assessments will be analyzed via a logistic regression model (similar to the logistic model above) that will be fit using the GEE approach (as implemented in PROC GENMOD in SAS) to account for correlation among repeated binary outcomes on the same individual. To examine the effect of dronabinol and clonidine on changes in risk for mood episodes during treatment and post-treatment follow-up, the logistic regression model will include the effects of treatment condition and the baseline measure of the outcome.

For studies involving treatment or diagnosis, provide information about standard of care at McLean (e.g., BWH, MGH) and indicate how the study procedures differ from standard care. Provide information on available alternative treatments, procedures, or methods of diagnosis.

The standard of care for cannabis dependence is psychotherapy; our treatment centers upon a medication.

Describe how risks to subjects are minimized, for example, by using procedures which are consistent with sound research design and which do not unnecessarily expose subjects to risk or by using procedures already being performed on the subject for diagnostic or treatment purposes.

Partners Human Subjects Research Application Form Version Date: July 26, 2016

Care will be taken to minimize risk. In addition to carefully screening prior to enrollment, we have scheduled regular laboratory visits during which we will carefully monitor response to medication or placebo with respect to side effects and changes in mood.

Describe explicitly the methods for ensuring the safety of subjects. Provide objective criteria for removing a subject from the study, for example, objective criteria for worsening disease/lack of improvement and/or unacceptable adverse events. The inclusion of objective drop criteria is especially important in studies designed with placebo control groups.

8.3.1.b. Safety Monitoring.

In order to monitor potential side effects from the initial dose of dronabinol, subjects will be observed at the laboratory facility for 4 hours following the following the first dose of the day in week 1. Subjects will come into the Behavioral Psychopharmacology Research Laboratory for monitoring by a research assistant and a study physician. This observation period is follows the SAMHSA guidelines for induction of buprenorphine, another agonist pharmacotherapy (CSAT 2004). Subjects will remain in the natural settings laboratory for a minimum of 2 hours and a maximum of 6 hours while having vital signs taken every 30 minutes. Subjects will be allowed to leave the facility by cab after being cleared by a study physician. Subjects will be allowed to leave the facility if they have 1) pulse rate greater than or equal to 50 beats per minute or less than or equal to 135 beats per minute; 2) blood pressure less than or equal to 140/90 and greater than or equal to 90/50; and 3) Behavioral Activity Rating Scale (BARS) score of less than 6. If pulse is decreasing, blood pressure is increasing, or BARS is increasing at the 2-hour assessment, the subject will remain an addition 30 minutes until the trend for these parameters is in the correct direction and the subject meets criteria for medical clearance.

During the 10-week treatment period, subjects will be seen for a MM visit and for urine screen visit. Medication compliance and side effects will be monitored at all visits. The initial visit in week 1 will include a monitored administration of medication described above. Subjects will have follow-up visits at 5, 10 and 14 weeks that will include a urine screen, blood sampling for laboratory testing, as well as evaluation for medication side effects.

Stopping Criteria. New psychotic symptoms thought to be related to dronabinol administration that are present at any pre-dose assessment or that remain present at the end of a 2-hour monitoring period will result in stopping of dronabinol. Clonidine stopping criteria include bradycardia less than or equal to 50 bpm, supine blood pressure of less than or equal to 100/65, a seated blood pressure of less than or equal to 90/60, or orthostatic change of >20 systolic or >10 diastolic on standing, at screening or any pre-dose assessment, or symptoms attributable to low BP (i.e. lightheadedness or dizziness on standing). Adverse events or side effects resulting from administration of either dronabinol or clonidine that persist beyond 7 days will warrant a call to the subjects PCP if they have one, and a decision will be made by the study physician about possible continued participation. If the subject is stopped, they will be followed for follow-up visits only.

Clinically significant lab abnormalities (liver function tests ≥3X normal, for example) will be rechecked immediately and, if determined to be clinically significant by the study

Partners Human Subjects Research Application Form

Version Date: July 26, 2016

physician, the subject will be removed from the protocol and followed for follow-up visits only. Worsening psychotic symptoms that predated study medication will warrant a call to the subject's psychiatrist and possible removal from the protocol if the patient is thought to be unstable by either the outpatient psychiatrist or the study physician. Similarly, suicidal ideation will warrant contact with the outpatient psychiatrist and possible removal from the protocol. Suicidal ideation with a plan will result in immediate removal from the protocol and the subject will be escorted by staff to the Psychiatric Emergency Room.

Events that may lead to stopping of the study include physiological side effects attributed to study medication such as seizure, psychomimetic reactions (hallucinations, paranoia, etc.), suicide, or other deaths. If any one of these occurs in 2 subjects, we will consider stopping the study if those effects can reasonably be associated with study participation. Due to the potential of dronabinol to lower seizure threshold, we will halt the study if 2 subjects have seizures during their participation. If any one besides seizure occurs in 3 subjects, we will halt the study.

FORESEEABLE RISKS AND DISCOMFORTS

Provide a brief description of any foreseeable risks and discomforts to subjects. Include those related to drugs/devices/procedures being studied and/or administered/performed solely for research purposes. In addition, include psychosocial risks, and risks related to privacy and confidentiality. When applicable, describe risks to a developing fetus or nursing infant.

The screening process and questions related to a subject's psychiatric history may cause discomfort. While dronabinol is FDA-approved for treatment of nausea related to cancer chemotherapy, subjects may experience side effects when taking nabilone, including hallucinations, paranoia, extreme fear; fast heart rate; feeling light-headed, fainting; or unusual thoughts or behavior. Less serious side effects are also possible including drowsiness, euphoria, weakness, lack of coordination; depression, anxiety, confusion, dry mouth; headache, trouble concentrating; insomnia. Subjects will also be informed that clonidine may cause drowsiness, dizziness, or lightheadedness associated with orthostatic hypotension. These effects may be worse if taken with alcohol or other medications that can cause drowsiness. Subjects will be warned not to abruptly stop taking clonidine.

EXPECTED BENEFITS

Describe both the expected benefits to individual subjects participating in the research and the importance of the knowledge that may reasonably be expected to result from the study. Provide a brief, realistic summary of potential benefits to subjects, for example, "It is hoped that the treatment will result in a partial reduction in tumor size in at least 25% of the enrolled subjects." Indicate how the results of the study will benefit future patients with the disease/condition being studied and/or society, e.g., through increased knowledge of human physiology or behavior, improved safety, or technological advances.

At the completion of this study, we hope to have improved our understanding of the relationship of the combination of dronabinol and clonidine on cannabis use.

Partners Human Subjects Research Application Form

Version Date: July 26, 2016

EQUITABLE SELECTION OF SUBJECTS

The risks and benefits of the research must be fairly distributed among the populations that stand to benefit from it. No group of persons, for example, men, women, pregnant women, children, and minorities, should be categorically excluded from the research without a good scientific or ethical reason to do so. Please provide the basis for concluding that the study population is representative of the population that stands to potentially benefit from this research.

Men, women, and minorities will all be recruited. Pregnant women and children will be excluded in part due to the lack of data on the safety of dronabinol in these groups.

When people who do not speak English are excluded from participation in the research, provide the scientific rationale for doing so. Individuals who do not speak English should not be denied participation in research simply because it is inconvenient to translate the consent form in different languages and to have an interpreter present.

Proficiency in English is necessary for a long-term treatment study that includes 10 MM sessions and ensures that the participants can properly convey any subtle side effects that relate to their safe participation in this study.

RECRUITMENT PROCEDURES

Explain in detail the specific methodology that will be used to recruit subjects. Specifically address how, when, where and by whom subjects will be identified and approached about participation. Include any specific recruitment methods used to enhance recruitment of women and minorities.

- 9. Human Subjects and Recruitment Strategies:
- 9.1. Sample Size: In order to meet the target sample of 18, We plan to screen 50 subjects ages 18-45 in the course of 20 months to achieve our desired sample size.
- 9.2. Advertising: Subjects will be recruited via websites, newspaper advertisements, flyers on campus, word-of-mouth, and the Psychotic Division Clinical Research Core. We will not specifically recruit subjects from particular patient units at McLean. Subjects may not be inpatients at McLean at the time of their participation in the study.

9.3. Inclusion criteria Inclusion:

1) Age range 18-45 years; 2) DSM-IV diagnosis of cannabis dependence, based on the Structured Clinical Interview for DSM-IV (SCID); 3) DSM-IV diagnosis of an Axis 1 psychiatric disorder, based on the Structured Clinical Interview for DSM-IV (SCID); 4) express a desire to quit cannabis use within the next 30 days; 4) have used cannabis on 20 days within the past 30 days (i.e., an average of 5 day per week); 5) identify cannabis as their primary drug of abuse; 6) stable on antipsychotic medication for 1 month; 7) for women of childbearing age, a negative pregnancy test at screening with agreement to use adequate contraception to prevent pregnancy and monthly pregnancy tests; 8) consent for us to communicate with their prescribing clinician if one exists; 9) furnish the names of 2 locators, who would assist study staff in locating them during the study period; 10) live close enough to McLean Hospital to attend study visits; 11) plan to stay in the Boston area for the next 3 months; 12) are willing and able to sign informed consent; and 13) must be psychiatrically stable, with no psychiatric medication changes in the 4 weeks prior to their screening visit.

Partners Human Subjects Research Application Form

Version Date: July 26, 2016

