Subjects will be instructed to keep us informed of any medications initiated after their enrollment in the study. Subjects will be reminded of the potential for additive CNS depression resulting from concomitant use of dronabinol and alcohol, opioid analgesics, benzodiazepines, and barbiturates. They will be warned initially of these potential additive effects during the informed consent process. Participants will be warned not to drive, operate machinery, or engage in any hazardous activity while receiving dronabinol. Subjects will also be informed that clonidine may cause drowsiness, dizziness, or lightheadedness associated with orthostatic hypotension. These effects may be worse if taken with alcohol or other medications that can cause drowsiness. Subjects will be warned not to abruptly stop taking clonidine.

Partners Human Subjects Research Application Form

Subjects will also be informed that data on the use of antipsychotic medications and dronabinol and/or clonidine is lacking. Due to the potential for sedation and possible hypotension in subjects taking these medications together, we will monitor carefully for these symptoms while educating subjects about these possible side effects.

- 8.2.1.b. Informed consent. Eligible subjects will complete standard consent documentation. Prior to the volunteer being asked any question about his/her health, the volunteer will be given a consent form to read. The research assistant will go over it in detail with the volunteer. After a physician investigator answers any questions the volunteer may have concerning the study, he/she will be asked to provide their informed consent to the licensed physician investigator. If enrolled in the study, consent to communicate with their other clinicians will be obtained. Clinicians will be notified of their patients' enrollment in the study, thus allowing them to carefully monitor for changes in mood while they are undergoing treatment to stop use of cannabis.
- 8.2.1.c. Randomization. Research staff will stratify subjects according to their self-reported frequency of cannabis use in the past 30 days: 1) daily use; and 2) non-daily use. The stratification procedure will guard against the possibility that one of the experimental conditions (i.e., dronabinol-clonidine or placebo) will be overrepresented by daily users, while non-daily users will predominantly be randomized into the other condition.

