- 8.2.1.d. Availability and Flow of Subjects into Treatment. We plan to screen 50 subjects in the course of 20 months to achieve our desired sample size.
- 8.2.1.e. Study Visits. Following eligibility for the study (as determined by the baseline-1 visit), subjects will come to the laboratory for a baseline-2 visit to complete research assessments, provide a urine sample, and begin daily diaries and Actiwatch (see Section 8.5.2.a.) Subjects will then come to the clinic twice a week during the study medication treatment phase. One visit will include a medical visit (dispensing of pills and Medical Management; see Sections 8.3.1.b, 8.3.2) and research assessments, including a urine screen (see Section 8.5.2.a and Table 8.2). The other visit will consist only of a urine screen (see Section 8.5.2.a). After the 10-week treatment period, participants will have a follow-up assessment visit at 14 weeks. Subjects will also come in once weekly during weeks 11, 12, and 13 following the 10-week treatment period to provide a urine sample, and hand in daily diaries/actiwatch.

Subjects will be randomized to receive either dronabinol and clonidine or placebo. [name] or the research assistants will present 7 day prescriptions to the McLean pharmacy and the subject will receive blister packs containing 1 week of medication or placebo, separated into daily doses. Subjects will be asked to return unused pills at each weekly medical visit; study staff will then perform a pill count for the study record. All groups will receive capsules following the same schedule: 2 capsules three times daily for 10 weeks. Each capsule will contain either dronabinol, clonidine, or placebo. Subjects in the dronabinol-clonidine group will take 5 mg of dronabinol three times daily for 10 weeks (between 7:00-9:00 AM, 3:00-5:00 PM and 9:00-11:00 PM). Subjects in this group will also take clonidine 0.1 mg po bid (between 7:00-9:00 AM and 9:00-11:00 PM) for 8 weeks, followed by a taper to clonidine 0.1 mg po qhs for the last 2 weeks of

Partners Human Subjects Research Application Form

Version Date: July 26, 2016

the protocol. Subjects will be assessed for side effects prior to each dosing increase and the study physician will decide if increasing the dose as scheduled is appropriate. See Table 1 for a schedule of study visits.

Table 1	Cabadula	of Magazinas
i abie i	Scheaule	of Measures

Table 1 Schedule of Measures					
Measure	Baseline 1 and 2	•	_		Week 14

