8.5.2.b. Self-Report. We will use 3 methods of self-report in an effort to determine the most appropriate and effective method for use in this population. An ActiWatch-Score will be determined via compact, wrist-worn, battery-operated activity monitors that are excellent devices for monitoring multiple drug use, drug craving, and sleep/wake activity (Licata et al., under review). We will provide subjects with a packet of 1 page, selfaddressed, prepaid postage Daily Diary pages which subjects will be asked to fill out between 7:00 and 9:00 a.m. each day and hand them in during their weekly visits. The diary consists of a series of questions about marijuana and other drug use as well as eating habits. During weeks 11, 12, and 13 subjects will have 1 weekly Diary/Actiwatch visit to hand in their daily diaries, , provide a urine sample, and have their Actiwatch data downloaded. During the weekly visits, we plan to collect cannabis use data using the Timeline Follow Back (TLFB) (Sobel and Sobel 1992) protocol that was developed for alcohol.

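### No side-effect inquiry is scheduled at the week 11–13 visits after dosing ends, and two sections disagree on whether side effects are asked about at the mid-week treatment visit

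*Combined protocol and SAP*

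**What the plan says.** **End of dosing.** Section 8.2.1.e: "All groups will receive capsules following the same schedule: 2 capsules three times daily for 10 weeks". The active group "will take 5 mg of dronabinol three times daily for 10 weeks". Clonidine is given twice daily "for 8 weeks, followed by a taper to clonidine 0.1 mg po qhs for the last 2 weeks of" the protocol. Section 8.3 has dronabinol titrated up but describes no step down at the end.

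**Weeks 11–13.** Section 8.2.1.e has subjects attend once a week "to provide a urine sample, and hand in daily diaries/actiwatch". Section 8.5.2.b: "During weeks 11, 12, and 13 subjects will have 1 weekly Diary/Actiwatch visit to hand in their daily diaries", and adds a urine sample and an ActiWatch download. Both Subject Payments paragraphs label these as ActiWatch, diary and urine visits. The diary asks about drug use and eating habits (Section 8.5.2.b).

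**Where scheduled safety checks sit.** The adverse-event checklist and side-effect questionnaire belong to the weekly Medical Management (MM) visit (Section 8.3.2.a). So do vital signs and orthostatic-symptom questions (Section 8.3.1.c) and the physician's suicide-risk assessment (Safety Monitoring, Section 8.2.1.a). MM runs during treatment and comprises 10 sessions. Section 8.3.1.b adds side-effect evaluation at weeks 5, 10 and 14.

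**Mid-week treatment visit.** Section 8.2.1.e: "The other visit will consist only of a urine screen". Section 8.3.1.b, after naming both weekly visits: "Medication compliance and side effects will be monitored at all visits".

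**The concern.** The two parts differ in kind.

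The first is a gap in scheduled ascertainment. The weeks after both drugs end are a distinct exposure period, and the plan regards stopping as worth a caution: "Subjects will be warned not to abruptly stop taking clonidine" (Study Restrictions, repeated under Foreseeable Risks). Subjects are in front of staff each week, yet no visit description asks staff to enquire about side effects. Events would be solicited weekly on treatment and not again until week 14, so counts from the two periods would not be comparable.

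The second is a contradiction. Staff cannot hold a visit that is only a urine screen and also monitor side effects at it. How often subjects are asked affects how many events are found. This is a pilot of 18 subjects in which two or three events of a kind trigger consideration of stopping, or a halt (stopping text following Section 8.3.1.b), so the intensity of questioning should be fixed in advance and the same for everyone.

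**Working it through.** No sample-size or error-rate formula applies. The check compares the sections and does arithmetic on the schedule.

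**1. Last dose.** Clonidine: 8 weeks + 2 weeks of taper = 10 weeks. Dronabinol: 10 weeks. Both end at week 10.

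**2. Visit count, tested against the plan's own payment total.**

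| Item | Amount |
|---|---|
| Initial interview | $50 |
| Baseline-2 | $25 |
| Weeks 5, 10, 14 | 3 × $50 = $150 |
| Non-MM urine visits, first 5 weeks | 5 × $25 = $125 |
| Non-MM urine visits, last 5 weeks | 5 × $30 = $150 |
| Week 1 monitoring visit | $50 |
| Weeks 11, 12, 13 | 3 × $30 = $90 |
| Diary bonus (maximum) | $100 |
| **Total** | **$740** |

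This reproduces the stated $740. The schedule therefore contains 10 mid-week urine visits and 3 separate visits in weeks 11–13.

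**3. Post-dosing gap.** Week 14 − week 10 = 4 weeks between scheduled side-effect assessments, with 3 attended visits in between. Across 18 subjects with full attendance, that is 18 × 3 = 54 visits with no side-effect inquiry described. The time from last dose to week 14 is less certain. If the final 7-day pack is dispensed at the tenth MM session (an assumption), the last dose comes up to a week after that session and the interval is nearer 3 weeks. In that case the week 10 assessment precedes the last dose.

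**4. On-treatment frequency.**
- Following Section 8.2.1.e: 10 MM visits × 1 = about 10 occasions per subject (18 × 10 = 180 in all).
- Following Section 8.3.1.b: 10 MM + 10 mid-week = about 20 occasions per subject (18 × 20 = 360 in all).

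**5. Could Section 8.3.1.b cover weeks 11–13?** Its sentence sits in a paragraph that opens with the 10-week treatment period, and it pairs side effects with medication compliance, which has no meaning after dosing. If it were stretched to weeks 11–13, it would conflict with Sections 8.2.1.e and 8.5.2.b there too.

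**6. Table 1.** In the text available, the header of one column that marks adverse events is not legible. Its urine entry carries the footnote for twice-weekly collection during treatment, whereas weeks 11–13 have one urine visit a week. Craving and withdrawal, marked in the same column, are described in Section 8.5.2.c as weekly on treatment and at week 14. The column is best read as weekly treatment visits, leaving none for weeks 11–13. That is an inference, and the gap stands on the section text without it.

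**The case against.** **The clonidine warning is already answered.** It concerns abrupt stopping, and the plan tapers clonidine over two weeks while MM visits with vital signs continue. This stands. A reader might infer that the plan disregards its own warning. For clonidine the documents do not support that, and they name no harm after a completed taper. For dronabinol no taper is described, but neither is a warning about stopping it.

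**Weeks 11–13 are not without safety cover.** On-call cover runs throughout the trial, clinical emergencies are evaluated medically, and the plan promises a low threshold for further workup when symptoms are reported. Pregnancy testing is tied to each urine sample and may apply in these weeks. Vital signs, adverse events and the C-SSRS are all marked at week 14. This also stands. It would be wrong to say that nothing is captured, that blood pressure after dosing goes unmeasured, or that recall is the only route. But on-call cover and emergency care respond to a problem already raised, and none of these provisions is a scheduled side-effect inquiry.

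**The mid-week conflict is small.** The structured forms belong to the MM visit, so monitoring mid-week need not mean a second form. Section 8.9 plans no adverse-event analysis, and either reading applies equally to both blinded arms. This is fair: the documents show no between-arm bias. The instruction to staff is still contradictory.

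**Adding vital signs and the C-SSRS would be a design preference.** This is accepted. The sections describing weeks 11–13 agree with one another, and no physician is described at those visits.

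**Conclusion.** The point holds, in two limited parts. No side-effect inquiry is scheduled between week 10 and week 14 although three in-person visits fall in that interval, so events there depend on spontaneous report, on-call contact or week 14 recall. On treatment, Sections 8.2.1.e and 8.3.1.b contradict each other, which makes the number of side-effect inquiries about 10 or about 20 per subject.

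The consequence is uneven ascertainment between periods, and possibly between staff. It is not bias between arms, and the efficacy analyses are unaffected. The conclusion assumes that the visit descriptions are meant to be complete and that the partly illegible Table 1 column refers to weekly treatment visits. It does not rest on any particular view of what stopping these drugs does, and it does not establish that vital signs or suicide assessment must be added. The change is worth making because it alters what safety data are collected at very little cost.

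**What to change.** 1. Reconcile Sections 8.2.1.e and 8.3.1.b so that both give the same content for the mid-week treatment visit. If side effects are to be asked about there, state how and on which form.
2. Add the adverse-event checklist and the side-effect questionnaire from Section 8.3.2.a to the visits in weeks 11, 12 and 13. State this identically in Sections 8.2.1.e and 8.5.2.b, and give those weeks their own column in Table 1.
3. The sponsor should decide, and state, whether vital signs and the C-SSRS are also collected at those visits. This review proposes no answer.

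**Cost.** The questionnaire takes 2 minutes by the plan's own figure, so 3 visits add 3 × 2 = 6 minutes per subject, plus the checklist, for which the documents give no time. No new instrument or visit is needed for items 1 and 2, only amendment wording. Item 3 could cost more, because no physician is described at those visits.
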